Self Tanner-Stage Questionnaire: Administration of a questionnaire designed to capture subject's Tanner stage of puberty. Age at Menarche will also be collected for the girls. DAISY subjects  $\geq 8$  years of age will be asked to complete this questionnaire. Girls will be asked to complete the female Tanner staging questionnaire, and boys will be given the male Tanner staging questionnaire to complete. These questionnaires will be given and collected at clinic visits, and will not be mailed to subjects.

Prostaglandins: Prostaglandins are lipid molecules derived from arachidonic acid via the enzyme cyclooxygenase PG synthase (PGS). The pro-inflammatory prostaglandins (PGE2) produced by macrophages and monocytes expressing PGS2 are potent modulators of the immune response and tolerance mechanisms. Ingestion of fish oils that contain n-3 PUFAs will result in a decrease in membrane arachidonic acid levels and a concomitant decrease in the capacity to synthesize prostaglandins from arachidonic acid (Calder, 1998). Prostaglandins (PGE2) will be measured in serum from subjects using ELISAs specific for each eicosanoid. Using these data, we will be able to see whether prostaglandin levels are associated with risk of BCA.

Physical activity: As DAISY subjects approach puberty we are interested in examining factors related to insulin resistance, such as weight and physical inactivity. To measure these factors we will collect a waist circumference on each participant and a short questionnaire on physical inactivity.

Puberty Hormones: Inhibin B, Testosterone, and Estradiol will be measured in blood samples from subjects in order to determine the onset and progression of puberty.

Cytokines: Adiponectin, Leptin, Interleukin-6, Interleukin-8, Monocyte Chemotactic Protein 1, Tumor Necrosis Factor Alpha, and Interferon gamma will be measured in stored plasma samples. Using this data, we will be able to examine whether obesity-related inflammation, insulin-resistance and beta-cell toxicity are related to IA and T1D.

Nutrient Biomarkers Vitamins, carotenoids, and red blood cell membrane fatty acid content will be measured on stored blood samples, in order to obtain a biological measure of nutrient exposure.

Oxidative Stress F2 isoprostanes will be measured on stored urine.

Development of automated reliable high-throughput methods, using dried blood spots, to screen for the autoantibodies against GAD65 and ICA512

Venipuncture, separation of serum or plasma, and frozen storage of the material are important limitations for large-scale population screening for autoantibodies. The filter paper technology using dried blood has been employed in automated screening for antibodies to HIV-1. Islet autoantibodies are remarkably stable in dried blood spots and the volume required for the recombinant GAA/ICA512AA radioassays is well within the range of 50-100  $\mu$ l of whole blood contained in a standard "Guthrie spot", collected in routine genetic newborn screening programs nationwide. To pilot the feasibility and accuracy of GAA and ICA512AA testing using dried blood spots, we collected blood samples from 46 T1D patients with a wide range of positive GAA and ICA512AA levels and from eight healthy controls. Coded sera obtained from these 54 persons were tested for GAA and ICA512AA using our routine combined assay. In addition, a few drops of capillary blood were collected from each of these 54 person on standard filter paper cards used by Colorado Newborn Screening Program (coded differently than serum), dried, stored at room temperature for a few days and then in 4° C for over a month. A standard piece of the whole blood blot, representing approximately 10  $\mu$ l of serum, was eluted using the standard GAA/ICA512AA assay washing buffer, and the autoantibodies were measured in the eluent using the routine method. Specificity of the dried whole blood method was 100% for both GAA and ICA512AA, compared to the routine method using serum. Sensitivity for GAA was lower only for those samples that were weakly positive in our routine assay (below 5 SD score of mean of 205 controls). Sensitivity for ICA512 antibodies was 94% (1/23 of patients false negative by filter paper assay). The correlation (Spearman) with the routine method was  $r=0.89$  for GAA and  $r=0.94$  for ICA512 ( $p<10^{-6}$  for both). Based on this pilot study, we are confident that we can accurately measure GAD65 and ICA512 autoantibodies using dried blood filter paper spots.

The filter paper method will be used in all cases where a sufficient amount of venous blood cannot be obtained, where there is a strong parental or child's preference for capillary vs. venous blood collection, or where blood is collected in a remote location, rather than in the DAISY or Kaiser Permanente clinic, and there is a strong preference on the part of the family or health provider collecting/shipping the blood sample, for filter paper vs. venous blood sample. Using estimated loss to follow-up we expect that 75% of the siblings and offspring otherwise lost ( $n=94$ ) and 50% of the lost general population participants in the existing ( $n=117$ ) and new ( $n=105$ ) cohorts will accept this alternative. This will significantly reduce loss of the follow-up outcome information. In addition, if the filter paper method is highly valid and reliable (as expected) and as predictive of strong islet autoimmunity progressing to diabetes as the currently used combination of GAA, ICA512AA and IAA, this new method would provide an attractive inexpensive alternative for large general population screening programs.

Continuous Glucose Monitoring (CGM)

IA subjects or those that have had an HbA1c test  $>5.7$  will be asked to complete a 7-10 day period of CGM up to 4 times per year. The study will also recruit participants negative for diabetes autoantibodies matched by age and gender to the cases to compare CGM results to subjects with positive autoantibodies

A CGM transmitter and receiver, sensors and in-person training by the study research nurse will be provided to the study participants at the Barbara Davis Center pediatric clinical research center on the day of the visit. In addition, the research nurse will be available by pager to answer questions during the 7-10 days of CGM. Certain medications are not allowed for one day prior to and during the time of CGM measurement. Acetaminophen (paracetamol, Tylenol) is prohibited for one day prior to and during the time of CGM measurement. glucose levels by measuring and transmitting glucose information from interstitial fluid every 5 minutes to the pager-sized receiver, which is kept in a pocket or clipped onto a belt of the subject. The CGM monitoring will be blinded to the subject

during the 7-10 day period. The results will be reviewed by a study physician at the end of monitoring for patient safety.

Measures of glucose control will include HbA1c, the overall mean of glucose values, % of values within target range (70-180 mg/dl), % of values <70 mg/dl (hypoglycemic range), and % of values >180 mg/dl (hyperglycemic). Primary variables to characterize glycemic variability will include the overall standard deviation (SD), the mean of daily differences (MODD) and the mean amplitude of glycemic excursions (MAGE). While multiple additional computed measures have been proposed in this dynamically evolving analytical field, they do not appear to offer a particular advantage and we will limit the number of comparisons to minimize the chance of type I error.

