Islet autoantibodies to insulin (IAA), GAD65 (GAA), IA-2 (IA-2A), and ZnT8 (ZnT8A) were measured at all visits and if positive, in 3-6 month intervals. IA is defined as the presence of one or more of the autoantibodies on at least two consecutive visits 3-6 months apart or development of T1D after a positive test. Diabetes is diagnosed using the ADA criteria.

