**Quality control** All samples with GAA or ICA512AA levels exceeding the 99th percentile of the distributions in 198 unrelated non-diabetic persons ages 0.4 - 67.5 years (i.e., GAA >0.032 and ICA512AA>0.16, respectively) and a random 10% of the remaining samples are blindly retested for quality assurance. The IAA testing were repeated if the levels are above 79 nU/ml, rather than above the 99th percentile of non-diabetic distribution (42 nU/ml) because of the large serum required relative to that obtained in these young children. With development of IAA microassay, all positive samples (index >0.01) are re-tested using blinded duplicates.

Primary endpoint for these analyses will be islet autoimmunity (IA) defined as presence of at least one autoantibody (IAA, GAA, ICA512AA), measured according to the protocols described in Specific Aim 1. All such children identified in the sibling/offspring cohort and in the newborn cohort are eligible. The two cohorts will not be combined for analyses. Persistent autoimmunity is defined as presence of at least one autoantibody on at least two separate blood tests. T1D, defined according to the WHO criteria is a secondary endpoint. Hemoglobin A1c and random blood glucose are measured with each blood sample in children positive for any islet autoantibody and the results are reviewed by pediatric diabetologist. If the value is >6% (nl 4.3-6.4%), the parents are asked to measure several fasting and 1-2 hr post prandial blood sugars at home. If the fasting glycemia is over 120 mg/dl and/or the post-prandial levels are >180 mg/dl on a home glucose monitor, a standard 2 hr oral glucose tolerance test is performed. Families of children persistently positive for more than one autoantibody are provided with keto-diastrix strips and taught how to test urine for presence of glucosuria and ketonuria.

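### Dried blood spots test only GAA and ICA512AA, so a negative spot does not exclude islet autoimmunity in participants kept in follow-up this way

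*Protocol*

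**What the plan says.** The Specific Aim 1 Approach describes a four-antibody panel: "Islet autoantibodies to insulin (IAA), GAD65 (GAA), IA-2 (IA-2A), and ZnT8 (ZnT8A) were measured at all visits". The outcome follows from it: "IA is defined as the presence of one or more of the autoantibodies on at least two consecutive visits 3-6 months apart", or T1D after a positive test. Section IV.A and the quality-control text in section IV.D use three antibodies. In the latter the primary endpoint is "defined as presence of at least one autoantibody (IAA, GAA, ICA512AA", and persistence there means two separate blood tests, with no requirement that they be consecutive.

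The filter-paper subsection of IV.D is headed "Development of automated reliable high-throughput methods, using dried blood spots, to screen for the autoantibodies against GAD" and goes on to name ICA512 as the second target. Its pilot compared spots with serum in 46 T1D patients and eight healthy controls, for those two antibodies. It reports: "Sensitivity for GAA was lower only for those samples that were weakly positive in our routine assay".

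The subsection then sets an operating rule: "The filter paper method will be used in all cases where a sufficient amount of venous blood cannot be obtained". The rule also covers family preference for capillary blood and remote collection. The protocol expects 75% of siblings and offspring otherwise lost (n=94) and 50% of lost general-population participants (n=117 existing, n=105 new) to accept, and concludes: "This will significantly reduce loss of the follow-up outcome information".

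**The concern.** The sentence on reduced loss treats a spot visit as a visit at which the outcome was observed. For IA that is only partly true. A child whose only antibody is IAA or ZnT8A cannot be classified as having IA from spots. A child whose first antibody is one of these gets an onset date only when GAA or IA-2A appears, if it ever does.

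Under the consecutive-visit definition, a spot visit between two serum visits can also interrupt a run of IAA or ZnT8A positivity, so that persistent IA is recorded as transient. That bears on Hypotheses 1.1 and 1.2, which concern persistent and transient IA respectively: children with persistent IA would move into the group expected to carry no excess diabetes risk. A missed first positive also means the child is not placed on the 3-6-month visits at which persistence is confirmed.

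**Working it through.** **1. Panel against definition.**

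| Place in protocol | Antibodies |
|---|---|
| Aim 1 Approach, IA definition | IAA, GAA, IA-2A, ZnT8A; any one suffices |
| IV.A and IV.D quality control | IAA, GAA, ICA512AA; no ZnT8A |
| IV.D filter-paper method | GAA, ICA512AA |

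The spot method covers two of four, or two of three, of the qualifying antibodies. IAA is outside it either way. The protocol itself contrasts spots with a panel that includes IAA: "as the currently used combination of GAA, ICA512AA and IAA". Nothing describes IAA or ZnT8A testing on spots. The IAA microassay in IV.D uses 5 µl of serum, but is not said to be run on dried blood.

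**2. Share of IA at risk of being missed.** Aim 1 (risk with a single autoantibody) states that 46% of IA in DAISY is persistently single-antibody. The split by antibody is not given.
- If none of it is IAA or ZnT8A: 0% missed.
- If all of it is: 46% missed.

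This range covers single-antibody IA only. Weak GAA positives, and children positive for IAA and ZnT8A but neither spot antibody, would add to it; the protocol gives no figure for either.

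**3. Late dating.** Section III states that 15% of late-onset and 32% of early-onset IA first present with multiple antibodies. So 100 − 32 = 68% of early and 100 − 15 = 85% of late IA do not. Where the first antibody is IAA or ZnT8A, spots date onset late or never.

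**4. Rough cross-check on panel coverage.** Workshop sensitivities in Aim 1 (Laboratory) are GAA 72%, IA-2A 62%, ZnT8A 62% and IAA 48%. Assuming independent assays, panel sensitivity = 1 − product of (1 − sensitivity):
- GAA + IA-2A: 1 − 0.28 × 0.38 = 89.4%
- adding IAA: 1 − 0.28 × 0.38 × 0.52 = 94.5%
- adding ZnT8A: 1 − 0.28 × 0.38 × 0.52 × 0.38 = 97.9%

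These are standardization-workshop figures, not sensitivities at IA onset, so they are only a guide.

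**5. Power.** The protocol's own figure first: N = 2,547, 9% IA, 20% lost, HR 0.66, two-sided 0.05, 80% power. Events = 2,547 × 0.09 × 0.80 = 183.4. With an assumed 1:1 split (Schoenfeld), power = Φ(√(d/4) × |ln 0.66| − 1.96) = 80.3%. The figure reproduces.

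Now add spot-followed participants back as followed. The forecast does not say whether its n values are acceptors (94 + 117 + 105 = 316) or those lost (0.75 × 94 + 0.5 × 222 = 181.5 acceptors). Without the new cohort the counts are 211 or 129.

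| Added | IA at 9% | Power, none missed | Power, 46% missed |
|---|---|---|---|
| 316 | 28.4 | 85.6% | 83.4% |
| 211 | 19.0 | 84.0% | 82.4% |
| 181.5 | 16.3 | 83.5% | 82.1% |
| 129 | 11.6 | 82.7% | 81.6% |

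Power falls by about two percentage points at most, assuming cases are missed equally in both groups. These counts illustrate the power effect; they do not estimate current spot use.

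**The case against.** The strongest reply is that the comparator is no data at all. Against complete loss, a two-antibody result does carry outcome information, and section IV.D puts GAD65/ICA512 coverage above 90% in newly diagnosed patients and in ICA-positive relatives followed to diabetes. That stands, but those people are at or near clinical disease. It says little about early or single-antibody IA, where the loss falls.

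The protocol also does not say how a spot negative is coded. A reader might infer that spot person-time enters the analysis as fully observed and negative. The document does not state this, and an unseen SAP may handle it. What the protocol does state is the collection rule, the claim that it preserves outcome information, and an IA definition that the rule cannot serve.

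Three further stronger readings are not supported:
- **A definite share of the cohort affected.** The forecast includes a new cohort and names a three-antibody comparator, while 2,547 is the cohort described today. Dividing one by the other mixes periods, and actual spot use is not reported.
- **Onset shifted across the age-6 split of Hypothesis 1.1.** Median age was already 17.2 years (IQR 13.5-20.2), and general-population births ended in mid-2006, so those children are at least 14 at the 2021 version date. Future spots cannot move their onset across age 6; only past use, which is not reported, could have.
- **Spot use as a marker of disengagement.** Insufficient venous blood and preference for capillary collection also trigger it.

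The broken-run problem is limited too. Antibody-positive children are seen every 3-6 months, section IV.E reports 85% of cases retained, and the two-separate-tests definition in IV.D does not require consecutive positives.

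**Conclusion.** The point holds in a bounded form. Followed as written, the filter-paper rule cannot detect IAA-only or ZnT8A-only IA, dates some onsets late, and can make persistent positivity look transient under the consecutive-visit definition. The claim that it preserves outcome information needs qualifying.

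The size is uncertain: 0 to 46% of IA among spot-followed participants through single-antibody disease, with the number of such participants unknown. The conclusion rests on reading the spot method as GAA and ICA512AA only, which is all the protocol describes. The change is worth making because it protects outcome classification at little cost, not because power is threatened.

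**What to change.** - In the filter-paper subsection of IV.D, state that spots ascertain GAA and ICA512AA only, and qualify the sentence on reduced loss accordingly.
- Record sample type with every antibody result, and code a spot negative as IA not determined.
- In the primary IA incidence and onset analyses, censor at the last full-panel serum sample whatever the later spot shows. The rule must be symmetric: counting spot positives as events while censoring spot negatives at the last serum sample makes censoring depend on outcome and biases incidence upward. State which panel counts as full, since the protocol uses both three and four antibodies.
- Use all spot results, including positives, in a sensitivity analysis.
- Do not let a spot negative break persistence in a child previously positive for IAA or ZnT8A.

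The cost is an endpoint sentence, a coding rule, some censored person-time and slightly wider intervals. Censoring also assumes that the move to spots is unrelated to IA risk given the model covariates; the sensitivity analysis gives a partial check on this.

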#### Blood Glucose meter

IA subjects or those that have had an HbA1c test >5.7 will be given a glucose meter to monitor blood glucose levels. The study doctor or study nurse will review the results from the meter and subjects will be notified if significant hypoglycemia or hyperglycemia is observed.

#### **Risks**

Genetically susceptible children are being currently identified by cord blood screening. Screening for genetic markers associated with (but not diagnostic for) a severe and currently incurable disease, such as T1D, raises important ethical issues. Our study placed special emphasis on: 1) voluntary participation ensured by informed consent process; 2) full disclosure of the results of the screening to parents, combined with education about T1D and genetic risk counseling; and, 3) confidentiality of genetic information that cannot be disclosed to health providers or other parties without parental consent. The informed consent process for the follow-up phase of the study has been and will continue to be separated from the consent to screen and involved additional genetic counseling. Since the prognostic significance of these markers is currently uncertain, psychologic support of the families will be made available as needed, so that undue anxiety about developing T1D is not invoked. Psychologic studies have found minor transient increases in anxiety with rapid appropriate coping for subject's positive for genetic or immunological risk markers and their relatives. Parents of only 6% of the children screened were concerned that a positive result of the screening could adversely affect the insurability of the child. Colorado law specifically prohibits insurance institutions from seeking and using results based on DNA testing for determination of eligibility of conditions of coverage.

Subjects: This is not a therapeutic/intervention study, and so we do not anticipate serious adverse events, however, for those children enrolled in the study, potential risks are from blood draws and psychological stress. The blood draw volume has been kept low, so that other than possible hematoma formation, minimal risks are foreseen. Participants may feel brief pain at the time of the needle stick for the blood draw. In about 10% of cases, a small amount of bleeding under the skin will produce a bruise (hematoma formation). The risk of temporary clotting of the vein is about 1% and the risk of infection of the bruise or significant external blood loss is less than 1 in 1,000. Occasionally, individuals may experience light-headedness or fainting during the blood draw process. This occurs in less than 1% of individuals undergoing a blood draw or blood donation. DAISY participants undergo blood draws in a phlebotomy chair with arm and back rests to minimize the risk of fall injury. If participants experience light-headedness or fainting during a blood draw, the reaction is documented and subjects are asked to lie down during subsequent blood draws.

There is the possibility of increased anxiety that may occur with the study of factors that could trigger T1D. Parents may become concerned that any illness or change in diet will be crucial. Extensive training of study staff in methods to counsel families has been instituted and ongoing since the beginning of the study. In addition, provision is made for access to counseling at the Barbara Davis Center, which is very experienced in dealing with these fears. These fears exist without this study. The participation in this protocol and the DAISY protocol may lessen such concerns, since children who test negative for autoantibodies are at lower risk of T1D, and since

children who become positive will be followed closely and counseled concerning the best treatment. Thus, the likelihood that diabetes will develop abruptly, leading to significant morbidity or mortality, will be lessened.

Continuous glucose monitoring (CGM) requires the insertion of a small plastic tube with a needle that is then removed. The small plastic tube stays in place for 7-10 days. There is a low risk of developing a local skin infection at the site of the sensor needle replacement. Itchiness, redness, bleeding and bruising at the insertion site may occur as well as local tape allergies.

The risk to loss of confidentiality is extremely low (none in 7 years with nearly 25,000 participants), computer files are accessible only to study staff with appropriate passwords, individual identifiers are kept in a separate file, all subject records are kept in ID access areas which allows entry only for staff with specific permission and all analyses are done anonymously.

#### Investigators

There are no known risks to investigators.

#### **Benefits**

There are no benefits to the subjects from participating in this research study. DAISY participants are compensated \$20 for each clinic visit.- Participants who complete the CGM procedure are compensated \$60 for each one-week wear period. Family members are compensated \$20 for a one time blood draw, to complete genetic HLA typing and T1D related autoantibody testing.

Based upon studies in identical twins, the genetic risk of developing T1D to an identical co-twin is approximately 20-30%. Thus, a large component of risk must be environmentally mediated. Since little can be done at present to modify genetic risk, further identification of environmental factors that could be modified through dietary advice or immunization (primary prevention) is imperative, even though it must include very young children, since this is the critical time period where the disease develops. Participation in this protocol allows for the earliest possible detection of pre-clinical diabetes amenable to intervention (secondary prevention). Risks and benefits associated with specific types of secondary prevention will be presented to interested parents. It will only be parents who will ultimately determine if these long-term benefits outweigh the short-term risks, through their participation.

These studies are critical for development of cost-effective population screening for T1D. The disease is a candidate for routine screening, because: 1) it is quite prevalent, affecting 0.5-1% in the U.S. population, but the clinical diagnosis is follows several years of asymptomatic autoimmunity with destruction of insulin producing cells; 2) it usually causes severe morbidity and premature death; 3) early detection is feasible using a sensitive and specific autoantibody tests; and 4) a number of early treatment protocols are being evaluated in large clinical trials involving relatives. The long-term health outcomes and cost-benefit ratio for early diagnosis have not been studied, because of the paucity of population studies, especially in the U.S.

